5.5.4 Special Concerns

The study investigators will meet on a weekly basis to discuss any issues or concerns with study procedures. If it is decided that the protocol needs to be amended or modified, the overall PI will make the necessary changes and submit an amendment to the DF/HCC IRB for approval. Once the amendment has been approved by the DF/HCC IRB, then the amendment will be submitted to the PCRC designated participating sites.

5.6 Adverse Reactions and their Management

5.6.1 Reporting Adverse or Unanticipated Events

Identification of adverse events may come through notification from the study participant, caregiver, clinician, or from review of the health record. In such circumstances, the PIs and investigative team will follow the following procedures:

Serious Adverse Events: Given that this study is PC intervention, we do not anticipate any study-related events meeting the FDA definition of a SAE (i.e., any fatal event, immediately life-threatening event, permanently or substantially disabling event, event requiring or prolonging inpatient hospitalization, or any congenital anomaly). This study population is comprised of individuals diagnosed with advanced lung cancer who frequently experience disease worsening, high symptom burden, and hospitalizations from the underlying disease and/or side effects of treatment. Therefore, as advanced lung cancer is a chronic-type terminal illness, regular fluctuations in cancer-related symptoms, disease worsening, hospitalizations, emergency department visits, and deaths are to be expected throughout the study, and we will not consider or report such events as SAEs in this trial.

Non-Serious Adverse Events: The IRB will be provided with unblinded summaries of study related non-serious adverse events by treatment group at the continuing reviews. These reports will include types of events, severity, and treatment phase. To date, we have had very few non-serious adverse events in our supportive care studies. Examples of potential non-serious adverse events are participants' discomfort with the study assessments or with their assignment group.

5.6.2 Anticipated Reactions

As this is a behavioral study, there are no ingested medications, and no biomedical procedures. Thus, participants will not be at any risk for physical harm due to their study participation.

Participants may find some of the questions asked in the questionnaire to be emotionally upsetting and may experience some fatigue from the length of the assessment battery.

5.6.3 Reaction Management

A detailed consent form will be signed by each participant following the explanations by the research team member or clinician. The consent form will include all study procedures, information about potential risks and benefits of participation, and information regarding whom the participant can contact for further questions. It also will state that participation is voluntary, that participants can refuse to answer any question, that they can withdraw from the study at any time, and that study participation is in no

way related to their medical care. All research team members will complete the required human subjects training before working on any human subject aspects of the study.

Should a participant exhibit or express distress, they will be reassured by the research team that they need not answer any questions they find upsetting. They will also be reminded that study participation is voluntary. If participants remain distressed, both the site PI and the primary oncology clinician will be notified. Should several participants express distress over an individual item, the research team will review the questionnaire and contact the IRB to consider removing it from the study.

If a participant reports severe distress or suicidal ideation during the study conduct, the research team member has a formal obligation to inform the site PI and/or patient's PC or oncology team. These clinicians will determine the need to involve psychiatry and take further action as deemed necessary. The research team will review sensitive items regarding suicidal ideation within 120 hours (5 business days) of receipt of completed surveys and will report any suicidal ideation to the site PI and/or patients PC or oncology team.

6.0 Ethical and Legal Issues

6.1 Confidentiality

Patient data will be collected at each participating institution using REDCap. Each site will maintain their own separate list of patient names and study ID's, which will be saved in password protected files. Participants will be identified on study forms by case number only to protect confidentiality. Identifiers such as name will only be used during the initial data retrieval process and can be destroyed once all data records have been obtained and data analysis has been completed as discussed previously. At the completion of the study, de-identified data files will be shared between the PCRC and MGH using a secure data transfer.

Participants' responses to survey questions will remain confidential unless there is active suicidal ideation confirmed by the research team. Under these circumstances, as clearly stated in the patient consent form, participants will be informed that the research team has a formal obligation to inform the site PI and/or a member of the patient's PC or oncology team. These clinicians will then determine the need to involve psychiatry and/or take further action as deemed necessary.

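### Protocol 5.6.3 has any suicidal ideation on a survey reported to the site investigator or clinicians, while 6.1 keeps it confidential unless it is active and confirmed

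*Protocol*

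**What the plan says.** Protocol 5.6.3 sets the procedure for surveys: "The research team will review sensitive items regarding suicidal ideation within 120 hours (5 business days) of receipt of completed surveys". It then says that the team "will report any suicidal ideation to the site PI and/or patients PC or oncology team". The trigger is any ideation. The section does not ask whether the ideation is active, and it sets no separate confirmation step before the report.

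Protocol 6.1 sets the confidentiality rule. Participants' "responses to survey questions will remain confidential unless there is active suicidal ideation confirmed by the research team". It goes on: "as clearly stated in the patient consent form, participants will be informed that the research team has a formal obligation" to tell the site investigator or a member of the patient's palliative care or oncology team. The exception therefore has two conditions, that the ideation is active and that the research team has confirmed it.

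Neither section refers to the other, and neither defines *active* or *confirmed*.

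**The concern.** A confidentiality section and a safety procedure that govern the same answers should have the same trigger. Here the safety procedure is unqualified and the confidentiality section is qualified, so staff who meet an answer showing non-active ideation cannot comply with both.

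Two things are at stake. The first is participant protection. Protocol 5.5.1 (Instrument Administration) allows surveys to be completed online, on paper at home or by telephone. For an online or mailed survey, the staff review may be the only route by which a clinician learns of the answer. Someone who applied 6.1 literally would not pass it on. The second is the clarity of the confidentiality undertaking, because 6.1 states a narrower exception than the procedure uses. SAP section 2 puts the number of participating institutions at 20, so the text should not leave each of them to choose between the two sections.

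**Working it through.** The plan gives no figure on this point, so there is nothing to recompute. The check is to set the two provisions side by side.

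| Element | Protocol 5.6.3 | Protocol 6.1 |
|---|---|---|
| Material covered | Completed surveys, items on suicidal ideation | Responses to survey questions |
| Recipients | Site investigator and/or the patient's palliative care or oncology team | The same |
| Kind of ideation | Any | Active only |
| Confirmation | None beyond the survey review | By the research team |
| Consequence if met | Must report | Confidentiality lifted, duty to inform |
| Consequence if not met | No report required | Answer stays confidential |

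**Step 1: do the rules overlap?** Yes. Both apply to completed surveys and both name the same recipients. 6.1 cannot be confined to disclosure outside the care team, because its own exception is about informing the site investigator and the treating clinicians.

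**Step 2: can *confirmed* be reconciled?** Yes. It can be read as the survey review that 5.6.3 already prescribes. On that reading confirmation adds no extra hurdle, and this word alone creates no firm conflict.

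**Step 3: can *active* be reconciled with *any*?** Not from the text. *Active* narrows the class and *any* does not. If the authors meant *active* only as *present*, the two sections would agree in intent. The protocol does not say so, and stating it would itself need an edit.

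**Step 4: apply both rules.**
- Active ideation, confirmed on review: 5.6.3 requires a report and 6.1 allows it. They agree.
- Non-active ideation on a survey: 5.6.3 requires a report and 6.1 keeps the answer confidential. They conflict.

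**Step 5: does another provision settle it?** None in the supplied text. The protocol's table of contents lists a Data Safety and Monitoring Plan, and 6.1 refers to the consent form. Neither is in the supplied text, and either may hold operating detail.

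**The case against.** The strongest reply is that this is a wording slip without practical effect. 5.6.3 is the specific, time-limited instruction that staff work from, and staff who follow it will report. It is also the more protective rule. The trial is late in its course: SAP section 2 describes enrollment of 1250 patients in the past tense. The SAP addendum entry of 2024-02-06 refers to data collection still under way for outcomes that need 48-week follow-up, and the entry of 2024-04-17 refers to peer review. An edit may reach few surveys. All of this stands, and it sets the grade. It does not remove the contradiction, because 6.1 still directs the opposite for non-active ideation and nothing ranks one section above the other.

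A reader might infer three further points that the documents do not support.

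- **That severe distress is caught in the same conflict.** 5.6.3 does say "If a participant reports severe distress or suicidal ideation during the study conduct, the research team member has a formal obligation to inform" the site investigator or clinicians. But its survey-review sentence covers only items on suicidal ideation. The duty on severe distress follows a paragraph about participants who show or voice distress to staff. Nothing tells staff to screen surveys for distress, and no cut-off is given. 6.1 covers survey answers only, so the two can be read together without conflict.
- **That participants were promised the narrower rule.** In 6.1 the reference to the consent form attaches to participants being told of the duty to inform. It does not show that the form repeats the word *active*, and the form cannot be checked here.
- **That the review window states two different limits.** The 120 hours with 5 business days in parentheses reads naturally as 5 × 24 = 120 hours counted on business days.

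**Conclusion.** The inconsistency is real and confined to one class of answer: suicidal ideation on a completed survey that is not active. Such an answer is reportable under 5.6.3 and confidential under 6.1, and the supplied text does not resolve it. For that class the text is contradictory as written, which is more than a missing detail.

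Its size is minor. The documents give no rate for such answers and no count of surveys outstanding, so no number of affected participants can be stated. A reader might infer that reports were missed, but nothing in the documents shows this. No endpoint, sample size or analysis depends on the point.

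The conclusion assumes that *active* carries its ordinary narrowing sense, and that neither the consent form nor the Data Safety and Monitoring Plan already settles which rule applies.

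**What to change.** In Protocol 6.1, replace the condition on active, confirmed ideation with: *any suicidal ideation identified by the research team (see 5.6.3)*. This brings the confidentiality section into line with the procedure, leaves the 5.6.3 trigger unchanged and supplies the missing cross-reference. Severe distress should not be added to the exception, since 5.6.3 gives no threshold for it on a survey.

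Then check that the consent form states the same condition. If it does not, correct it by the route in Protocol 5.5.4 (Special Concerns): an amendment approved by the DF/HCC IRB and then submitted to the participating sites.

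The cost is one amendment for a one-phrase change, and a slightly wider stated exception to confidentiality. The study data and the analysis are unaffected.

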7.0 Statistical Analysis

7.1 Primary Endpoint

To determine whether telehealth PC is equivalent to in-person PC for improving patients' QOL.

7.2 Secondary Endpoints

- 7.2.1 To determine whether telehealth PC is equivalent to in-person PC with respect to patient-clinician communication about EOL preferences.
- 7.2.2 To determine whether telehealth PC is equivalent to in-person PC with respect to length of stay in hospice.
- 7.2.3 To assess the superiority of telehealth versus in-person PC on caregiver

- participation in PC visits.
- 7.2.4 To assess the superiority of telehealth versus in-person PC on patient satisfaction.
- 7.2.5 To assess the superiority of telehealth versus in-person PC on caregiver satisfaction.

7.3 Exploratory Endpoints

- 7.3.1 To compare coping strategies in patients assigned to telehealth versus inperson PC.
- 7.3.2 To compare prognostic understanding in patients and caregivers assigned to telehealth.
- 7.3.3 To compare the effect of telehealth versus in person PC on caregivers' outcomes, including QOL and mood.
- 7.3.4 To compare the effect of telehealth versus in-person PC on patients' mood.

7.4 Sample Size and Power Calculation

The primary endpoint of the study is to establish that telehealth PC is equivalent to inperson PC in patient-reported QOL at week-24, as measured by the FACT-L. Although the primary endpoints in our previous studies assessed the change in FACT-L from baseline to week-12, we chose to focus on QOL at 24 weeks as the life-expectancy of patients with advanced lung cancer has increased over the last few years. In our most recent randomized trial of early integrated PC versus standard oncology care, we observed a 7.5 (SD = 17.0) point difference in the FACT-L at week-24 favoring the early integrated PC group. Thus, we chose a conservative equivalence margin of 4 points, which is slightly more than 50% of the previously observed advantage with early integrated PC compared to oncology care alone. As a 6-point difference in FACT-L score is considered the lowest range of a clinically meaningful difference, our equivalence margin would not reach the threshold of clinically meaningful difference in QOL between telehealth PC and in-person PC. 53 With 469 patients per group, we would have 95% power to establish the equivalence of telehealth PC compared to in-person PC on the FACT-L, with a two-sided alpha of 0.05, and an equivalence margin of 4 points. In our recent trial, we observed 25% missing data at 24 weeks. Therefore, we increased our sample size to 625 per group (total sample size = 1250 patients) to ensure we have adequate power to assess the equivalence of telehealth PC compared to in-person PC. Importantly, we chose to be conservative in estimating the sample size of this trial given the proposed testing of equivalence of telehealth PC to in-person PC on secondary outcomes as well as the planned subgroup analyses.

The proposed study will also have adequate power to assess for equivalence of telehealth PC compared to in-person PC in EOL communication and hospice length-of-stay. With a sample size of 1250, we will have 89% power, with a two-sided alpha of 0.05, to assess the equivalence of telehealth to in-person PC on patient-reported EOL communication with an equivalence margin of 8%, assuming the rate of EOL communication in the in-person PC group is 30% (based on our recent trial). With this sample size, we will also have 94% power to establish the equivalence of telehealth PC compared to in-person PC in hospice length-of-stay, with a two-sided alpha of 0.05, and an equivalence margin of 6

days (SD = 30.0). Given that this is an equivalence trial, we were conservative with the power estimations by using the highest observed standard deviation for all outcomes from our prior studies.

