We will examine patient-report of discussing EOL care preference with their clinicians using the following item: "Have you and your doctors discussed any particular wishes you have about the care you would want to receive if you were dying?" (Yes/No). Although patients will complete this measure repeatedly during the study, we will use the final assessment for this analysis. We will assess differences between study groups in the rate of patients reporting "Yes" to this item using a Fisher's exact test with a two-sided alpha of 0.05 (equivalence margin=8%). We will then use a logistic regression model adjusting for any demographic and clinical factors that are imbalanced to assess differences in this dichotomous outcome between the two groups.

Additionally, we will assess the equivalence of hospice length-of-stay between telehealth PC and in-person PC with an equivalence margin of 6 days. We will use linear regression models adjusting for demographic and clinical factors as necessary to compare hospice length-of-stay between telehealth PC and in-person PC. Although hospice length-of-stay is not normally distributed, based on a sample size of 1250, the means would have a normal distribution (central limit theorem). Nonetheless, we will also perform poisson regression or Wilcoxon rank sum test to compare our results to those obtained with linear regression.

Aim 3: To compare the effect of telehealth versus in-person PC on caregiver participation in PC visits and outcomes

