PHQ-9	Pt only	BL, 12, 24, 36, and 48	Range: 0-27 (Higher
		weeks	scores indicate more
			severe depression)
Brief Cope	Pt only	BL, 12, 24, 36, and 48	Range for each facet:
		weeks	2-8 (Higher scores
			indicate more
			engagement in coping
			style)
Support Service Utilization	Pt only	24 weeks	
HADS	Pt & Cg	BL, 12, 24, 36, and 48	Range for each
		weeks	domain: 0-21 (Higher
			scores indicate more
			severe
			depression/anxiety)
Satisfaction with Care Delivery	Pt & Cg	12, 24, 36, and 48	
Questionnaire		weeks	
CARGOQOL	Cg only	BL, 12, 24, 36, and 48	Range is 0-100
		weeks	(Higher scores
			indicate better quality
			of life)
Caregiver PTPQ	Cg only	BL, 12, 24, 36, and 48	
		weeks	
After Death Assessment	Cg only	3 months after patient	
		death	

Pt (patient); Cg (caregiver); BL (Baseline); SCQ (Self-Administered Comorbidity Questionnaire); FACT-L (Functional Assessment of Cancer Therapy-Lung); PTPQ (Perception of Treatment and Prognosis questionnaire); PHQ-9 (Patient Health Questionnaire); HADS (Hospital Anxiety and Depression Scale); CARGOQOL (CareGiver Oncology Quality of Life)

The **primary outcome** is the patient-reported quality of life at 24 weeks from enrollment, as measured by the FACT-L.

The **secondary outcomes** are:

- Patient report of patient-clinician communication about EOL care preference using the following item on the PTPQ: "Have you and your doctors discussed any particular wishes you have about the care you would want to receive if you were dying?" The patient's final assessment will be used.
- 2. Patient length of stay in hospice (in days) among patients who die during the study, as documented in the EHR.
- 3. Caregiver attendance in PC visits, per PC clinician documentation in the post-visit electronic survey.
- 4. Patient satisfaction with care as measured by the Satisfaction with Care Delivery Questionnaire. The patient's final assessment will be used.
- 5. Caregiver satisfaction with care as measured by the Satisfaction with Care Delivery Questionnaire. The caregiver's final assessment will be used.

The **exploratory outcomes** are:

- 1. Rate of change in patient quality of life from baseline to week 48, as measured by the FACT-L.
- 2. Patient coping strategies at 24 weeks, as measured by the Brief-COPE Questionnaire
- 3. Rate of change in patient coping strategies across all study time points, as measured by the Brief-COPE Questionnaire.

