The difference between groups in the proportion of patient-clinician communication about EOL care preference at the final follow-up assessment will be assessed using a generalized linear regression model specified with an identity link function and binomial response probability distribution. The model will include group assignment (telehealth PC vs in-person PC) as a main effect. Using the pre-specified equivalence margin of ±8%, the nominal p-value for equivalence will be calculated as the larger of the two p-values from two one-sided tests of the estimated difference in proportions against null values of -8% and 8%. Equivalence of in-person PC will be established if the nominal p-value is significant after application of the multiplicity adjustment procedure for secondary outcomes. Model-based estimates of the proportion with 95% CI in each group, the difference in proportions between groups and its 90% CI, the nominal p-value, and the multiplicity-adjusted p-value will be reported.

The difference between groups in the mean length of stay in hospice among patients who die during the study will be assessed using a linear regression model with a main effect for group assignment (telehealth PC vs in-person PC). Using the pre-specified equivalence margin of ±6 days, the nominal p-value for equivalence will be calculated as the larger of the two p-values from two one-sided tests of the estimated difference in means against null values of -6 and 6. Equivalence of telehealth PC will be established if the nominal p-value is significant after application of the multiplicity adjustment procedure for secondary outcomes. Model-based estimates of the mean with 95% CI in each group, the difference in means between groups and its 90% CI, the nominal p-value, and the multiplicity-adjusted p-value will be reported.

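### Protocol 7.4's secondary equivalence powers (94% hospice stay, 89% end-of-life communication) were never updated for the SAP's decedent-only set, two one-sided tests and multiplicity rule

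*Protocol*

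**What the plan says.** Protocol 7.4 opens the paragraph on secondary outcomes with "The proposed study will also have adequate power to assess for equivalence of telehealth PC compared to in-person PC", naming EOL communication and hospice stay. For communication it states "With a sample size of 1250, we will have 89% power, with a two-sided alpha of 0.05", with a margin of 8% and a 30% rate in the in-person arm. For hospice stay, taking a margin of 6 days and an SD of 30, it states "With this sample size, we will also have 94% power to establish the equivalence of telehealth PC compared to in-person PC in hospice length-of-stay".

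The protocol sets no restriction on who enters the hospice analysis. Section 7.2 says only "To determine whether telehealth PC is equivalent to in-person PC with respect to length of stay in hospice", and section 7.5 argues that "based on a sample size of 1250, the means would have a normal distribution (central limit theorem". For communication, section 7.5 names Fisher's exact test at a two-sided 0.05 next to the 8% margin.

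The SAP differs on three counts:
- **Analysis set.** SAP section 7 defines the hospice outcome as "Patient length of stay in hospice (in days) among patients who die during the study", and the model in section 10 uses the same set.
- **Test.** SAP section 10 takes as the communication p-value "the larger of the two p-values from two one-sided tests of the estimated difference in proportions against null values of -8% and 8" percent, reported with a 90% CI. Hospice stay is handled the same way against -6 and 6 days.
- **Decision level.** For both outcomes, section 10 declares equivalence only if the p-value is significant after multiplicity adjustment. The signed rule was Benjamini-Hochberg at a false discovery rate of 0.15 (SAP section 9). Addendum item 3(B) replaced it with Bonferroni at a family-wise 0.05 and gives no divisor.

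SAP section 8 gives power for FACT-L at week 24 and for nothing else, so Protocol 7.4 remains the only stated power for these two outcomes.

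**The concern.** A stated power is useful only if it belongs to the analysis that will be run. Here the analysis set of one outcome, the test of the other and the decision level of both are not those behind the stated figures. Each change lowers power relative to those figures, except that the signed Benjamini-Hochberg rule could have gone either way.

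The stake is interpretation. If equivalence is not shown for either outcome, readers will weigh that result against 94% and 89% and may take it as evidence of a real difference in care, when the planned analysis may simply have had less power than advertised.

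**Working it through.** **Formula.** For two one-sided tests (TOST) with no true difference, power = 2Φ(m/SE − z) − 1, where m is the margin and z is the normal quantile for the one-sided level: 1.645 at 0.05, 1.960 at 0.025, 2.326 at 0.01. A nominal 0.05 per side matches the SAP's 90% CI.

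**Inputs.** 625 per group; hospice margin 6 days and SD 30; communication margin 0.08 and rate 0.30, taken as true in both arms (Protocol 7.4). The number of deaths and the share of patients with no follow-up answer are not in the documents and are assumed below.

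**1. Hospice: the plan's figure.** SE = 30·√(2/625) = 1.697 days; m/SE = 3.536; power = 2Φ(3.536 − 1.645) − 1 = 94.1%. The stated 94% reproduces. The smallest n that reaches 94% is 622 per group, so the figure uses practically every randomised patient.

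**2. Hospice: decedents only.** Same formula, n = 625 × assumed share dying:

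| Share dying | n per group | m/SE | 0.05 per side | 0.025 | 0.01 |
|---|---|---|---|---|---|
| all | 625 | 3.536 | 94.1% | 88.5% | 77.3% |
| 90% | 562.5 | 3.354 | 91.3% | 83.7% | 69.6% |
| 80% | 500 | 3.162 | 87.1% | 77.1% | 59.7% |
| two-thirds | 416.7 | 2.887 | 78.6% | 64.6% | 42.5% |
| half | 312.5 | 2.500 | 60.8% | 41.1% | 13.8% |

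At 0.05 per side, 80% power needs 429 deaths per group, or 429/625 = 69%.

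**3. Communication: TOST.** SE = √(2 × 0.30 × 0.70/625) = 0.02592; m/SE = 3.086; power = 2Φ(3.086 − 1.645) − 1 = 85.0%. Exact binomial enumeration gives 85.2%. Reaching 89% would take 691 per group. If an assumed 10% have no follow-up answer (562.5 per group), SE = 0.02733, m/SE = 2.928 and power is 80.0%.

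**4. Where 89% may come from.** A two-sided Fisher's exact test at 0.05 with 625 per group has 88.7% power to detect 30% versus 22%. That matches the stated figure and the test named in Protocol 7.5, but it is the power to detect a difference, not to show equivalence. This origin is an inference; the 85% does not depend on it.

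**5. Decision level, all 1250 analysed.**
- Bonferroni over five outcomes, 0.05/5 = 0.01: communication 2Φ(3.086 − 2.326) − 1 = 55%; hospice 77%.
- Bonferroni over two outcomes, 0.05/2 = 0.025: communication 74%; hospice 88%.
- Superseded Benjamini-Hochberg at 0.15 over five: the per-test threshold runs from 0.03 to 0.15 depending on the other p-values, so communication power ran from 77% to 96%.

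The hospice figures here are upper limits, because they assume that every patient dies during the study.

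**The case against.** **Neither figure is a miscalculation.** A reader might infer that the power arithmetic is faulty. For hospice it is not: 94% is correct for the protocol's own plan. For communication, 89% agrees with the test that the protocol names. What stands is that these are powers for analyses other than those in the SAP.

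**The hospice loss may be modest.** A reader might infer that the hospice aim is badly underpowered. The documents do not support that, because they give no number of deaths. Protocol 5.4.1 collects utilisation data until death or 18 months after the last enrolment, which is a long window. As an illustration, assume exponential survival, uniform accrual over A months and F = 18 months of further follow-up; the share dying is 1 − e^(−λF)(1 − e^(−λA))/(λA), with λ = ln 2/median. With the one-year median that Protocol 1.2 gives for most patients, applied to all, and A = 36, the share is 1 − 0.354 × 0.421 = 85% and nominal power is 89%; with A = 60 it is 90% and 91%. If one-third of patients instead have a median of 24 to 48 months (Protocol 1.2 speaks of several years for responders), with A = 36, then 78% to 70% die and nominal power is 86% to 81%. Those values could fairly be called adequate, but only before multiplicity adjustment.

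**The 48-week remark is not a death window.** Addendum item 3(A) says that the first two secondary outcomes require 48-week follow-up. A reader might take this to limit hospice stay to deaths within 48 weeks. It explains why those outcomes are reported later, and it neither redefines the set nor withdraws Protocol 5.4.1. The two passages still need one stated cut-off.

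**Hospice patients are not lost to the communication outcome.** Protocol 5.4 stops questionnaires once a patient is on hospice, but the final available answer is used. Only patients with no follow-up answer drop out.

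**The SD may be cautious.** Protocol 7.4 says that it used the highest SD observed. To keep 94% with two-thirds dying, the SD would have to be 30·√(2/3) = 24.5 days; the documents give no lower value.

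**The practical effect is limited.** FACT-L set the sample size, enrolment is complete, and the SAP reports estimates with 90% CIs. That argues for a small fix rather than for none.

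**Conclusion.** The mismatch is certain; the size of the hospice loss is not. The 94% requires about 622 of 625 patients per group, whereas the SAP counts only those who die during the study. Nominal power is therefore 91% to 61% for assumed death shares of 90% to one-half. For communication, nominal TOST power is 85% rather than 89%, given 30% in both arms, no true difference and an answer from every patient.

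A reader might infer that 85% is simply the right replacement for 89%. It is not, because the SAP decides on the adjusted p-value. At the Bonferroni rule in force, the figures with all 1250 are 55% and at most 77% (five outcomes), or 74% and at most 88% (two outcomes). The Bonferroni rule dates from 2024 and is no fault of the original planning, but the stated powers no longer describe the rule that will be applied.

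This concerns two secondary outcomes and leaves the primary analysis untouched. It should be corrected because Protocol 7.4 claims adequacy without qualification and nothing elsewhere restates the figures.

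**What to change.** In an SAP addendum entry, or in Protocol 7.4:

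1. State the Bonferroni divisor for the secondary outcomes, and hence the per-test level.
2. Restate both powers at that level. Beside them give the values at 0.05 per side, labelled as nominal: communication 85%, with a range for patients who have no follow-up answer; hospice stay as a range by number of deaths.
3. State one cut-off for counting a death as during the study, so that Protocol 5.4.1 and addendum item 3(A) read consistently.
4. Qualify the claim of adequate power accordingly.

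The cost is a few sentences, and the stated powers become less favourable. No new patients, data or change of analysis is needed.
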